This proposal extends a pilot program called My Baby, My Move (MBMM; PI: [name]), funded by the Centers for Disease Control and Prevention aimed at developing and implementing a prenatal physical activity intervention to promote regular engagement in moderate-intensity physical activity. The development of the MBMM intervention stemmed from conducting individual and focus group interviews with over 65 pregnant women to better understand what facilitates and prevents engagement in prenatal physical activity [24]. The 8-week MBMM intervention was beta-tested on 66 pregnant women (n=33 MBMM intervention; n=33 educational control group) during mid-late second trimester throughout third trimester. Total physical activity (light, moderate, vigorous) increased in the intervention group by over 80 minutes from baseline to 3 months postpartum [294 min/wk (SD 89.8) to 373.1 min/wk (SD 146)] whereas the control group decreased over time [309 min/wk (SD 146.6) to 302 (SD 112.1)]. The intervention was also successful in increasing certain known mediators of physical activity, such as behavioral skills (e.g., self-regulation) [pre: mean 32.75(SD 8.8)//post: mean 39.33(SD 5.30) ($p=0.03$)] and social support [pre: mean 26.17 (SD 8.94)//post: mean 33.75 (SD 10.01) ($p=0.02$)]. The process evaluation for the MBMM program found high fidelity in intervention delivery, average attendance (88% for each session over an 8 week period) and high satisfaction with the program (1.3 on a 5 point scale, with 1 being extremely satisfied). A major limitation to these data is that we did not collect data on EGWG. Additionally physical activity data were self-report and standard of care was used as a comparison group. Although these data are encouraging and in the hypothesized direction, based on feedback from participant post-intervention qualitative interviews (unpublished) and current recommended evidence-based strategies, we are proposing to test an enhanced version of MBMM called MBMM+ that will 1) examine the impact of the intervention on EGWG, 2) add in-depth information on new topics related to mood (stress-management,

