Sample Size. In terms of intervention effects on EGWG, results have been variable across studies, with average intervention effects being small to moderate. In terms of physical activity, our preliminary work with the original MBMM showed an effect roughly equivalent to Cohen's $d = 0.69$. This effect falls into the moderate range, similar to higher-impact interventions on EGWG [27]. Based on these two effect ranges, we estimated effect size to detect effects of $d > .63$, a medium effect, for the proposed MBMM+ intervention. Using this effect size, $\alpha = .05$, and $1-\beta = .80$, a sample size of 40 per arm (80 total) would be adequate to detect medium effects in EGWG, exercise, and other outcomes. We propose enrolling 50 per arm to account for up to 20% attrition and to allow for power to detect potentially smaller effects for EGWG. This level of power is expected to also be adequate for detecting changes in mediators, which have previously been observed to be more powerfully affected by the MBMM intervention than physical activity.

Due to COVID-19, the trial will be run two times; a remote pilot of the trial will be run in the Fall of 2020 (n=30), followed by a larger in-person trial (pending COVID-19) in the Spring of 2021 (n=70)

C. Study Design and Research Methods

Intervention Group:

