Throughout the course of this study, we will provide for protection of human subjects. All protocols will be submitted for review and approval to the Colorado Multiple Institution Review Board (COMIRB). All personal data will be kept secure with personal identifiers and study identification numbers maintained in separate, secure, databases. Only the PI and Co-Is will have access. The proposed study is designed to women and overall, the findings of this study may potentially impact the health and wellbeing of women and children.

We have also designed the assessment procedures to minimize burden on participants. Participants will be compensated \$30 per survey completion (T1 and T3; \$60 total/participant). Participants will also receive tickets for a random drawing and chance to receive free diapers for their participation in T2 data collection. Pregnant participants in the MBMM+ intervention group will also receive a yoga mat and pedometer, and both control and intervention groups will receive drawings for free diapers. These types of incentives and amounts are consistent with our other studies at UCH. In addition to the yoga mat and pedometer, the intervention group participants will have the opportunity to keep a Fitbit. If participants attend all sessions 8-16, they will get to keep a Fitbit at the end of the program following post-data collection. If participants in the intervention program attend all but two sessions from sessions 8-16, they will be entered into a raffle for a Fitbit to keep at the end of the program following post-data collection.

F. Data Analysis Plan:

We will use latent growth curve models to separately examine intervention effects on 1) moderate-intensity exercise assessed by the Fitbit and 2) EGWG. These models will then be expanded to examine secondary outcomes (e.g., physical activity, mood, sleep quality, delivery outcomes) and mediators (e.g., exercise self-efficacy, social support, and behavioral skills). For all models, we will control for patient age, ethnicity, parity, risk status, and SES. Primary analyses will be conducted as intent-to-treat, although exploratory as-treated analyses may also be used. Analyses will be conducted primarily using SAS Version 9.2 and Mplus Version 6.0. In closing, the study's proposed approach

is scientifically sound using a tight, randomized controlled trial framework to reduce study bias and increase likelihood of reproducibility.

G. Summarize Knowledge to be Gained:

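### Adjusting the 12-week Fitbit comparison for the baseline Fitbit value would protect the 80% power at d = 0.63; the pilot effect quoted in support has no stated derivation and comes from a different measure and time point

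*Combined protocol and SAP*

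**What the plan says.** Protocol section IV.B (Sample Size) names two sources for the planning effect. One is published EGWG interventions, whose average effects it describes only as small to moderate. The other is the team's pilot, for which "our preliminary work with the original MBMM showed an effect roughly equivalent to Cohen's $d = 0.69" in physical activity. It continues: "Based on these two effect ranges", "we estimated effect size to detect effects of $d > .63$, a medium effect, for the proposed MBMM+ intervention". The size follows: "a sample size of 40 per arm (80 total) would be adequate to detect medium effects in EGWG, exercise, and other outcomes", at alpha 0.05 and power 0.80. Enrolment is 50 per arm to allow for 20% attrition.

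Section III reports the pilot (33 women tested per arm). Total activity (light, moderate and vigorous) from baseline to 3 months postpartum went from "294 min/wk (SD 89.8) to 373.1 min/wk (SD 146)] whereas the control group decreased over time [309 min/wk (SD 146.6) to 302 (SD 112.1". The same section lists limitations: no EGWG data were collected, and "physical activity data were self-report and standard of care was used as a comparison group".

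Section IV.F plans latent growth curve models for two lead outcomes, EGWG and "moderate-intensity exercise assessed by the Fitbit". The covariates are age, ethnicity, parity, risk status and SES. Section IV.A collects Fitbit data for 7 days at T1 (baseline) and T3 (12 weeks) only, and section IV.D places the T1 Fitbit week before randomisation.

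**The concern.** Two things needed checking.

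First, 0.69 is the only numerical effect in the paragraph, and it makes 0.63 look cautious. It has no derivation, and the pilot variable differs from this trial's activity outcome in method (self-report against Fitbit), content (all intensities against moderate intensity) and timing (3 months postpartum against 12 weeks post-baseline).

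Second, the 40 per arm matches a t-test on raw scores, whereas the analysis is a growth model on two Fitbit time points. IV.F does not say whether arm may affect the T1 level, and T1 Fitbit activity is not in the covariate list. That choice decides whether the T1 data add power or reduce it.

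Aim 2 is to supply effect-size estimates for a larger trial. A less precise activity estimate, or an unexplained 0.69 carried forward, would weaken that purpose.

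**Working it through.** **The plan's own figure.** Inputs from IV.B: d = 0.63, alpha 0.05, power 0.80. Sidedness is not stated. By the normal approximation, two-sided n is 40 per arm (one-sided would be 32), so two-sided is taken. Power at 40 per arm is 79.5% by the noncentral t and 80.4% by the normal approximation. Attrition: 40 / (1 - 0.20) = 50. The plan's figures reproduce.

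**What the pilot data give.** Inputs from section III. That these are the source of 0.69 is an inference, since IV.B does not say so, but no other pilot activity data are shown.

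- Follow-up difference: 373.1 - 302 = 71.1 min/wk.
- Difference in change: (373.1 - 294) - (302 - 309) = 79.1 + 7 = 86.1 min/wk.
- Pooled follow-up SD: sqrt((146² + 112.1²)/2) = 130.2.
- Pooled baseline SD: sqrt((89.8² + 146.6²)/2) = 121.6.
- All four SDs pooled: 125.9.

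| Definition of d | Value |
|---|---|
| Follow-up difference / follow-up SD | 71.1 / 130.2 = 0.546 |
| Difference in change / follow-up SD | 86.1 / 130.2 = 0.66 |
| Difference in change / all four SDs pooled | 86.1 / 125.9 = 0.68 |
| Difference in change / baseline SD | 86.1 / 121.6 = 0.71 |
| Difference in change / SD of change, r = 0.55 assumed | 86.1 / 124.4 = 0.69 |

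If all 33 per arm were followed up (section III gives only the number tested), the SE of 0.546 is sqrt(2/33 + 0.546²/132) = 0.25, and the 95% CI is about 0.05 to 1.04.

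**Sensitivity to d, unadjusted t-test.** At 0.546, power is about 67% with 40 analysed per arm and 77% with 50. At 0.63 with 40 it is 79.5%. At 0.69 with 40 it is 86%.

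**Sensitivity to how T1 is used.** Take the plan's d = 0.63 as a raw-score effect and assume equal SDs at T1 and T3. The documents do not give the T1 to T3 correlation r, so a range is shown. The effects of the other IV.F covariates are ignored.

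With two time points and arm free on both intercept and slope, the arm effect on slope is the difference in mean change. The effective d is 0.63 / sqrt(2(1 - r)). Adjusting T3 for T1 gives 0.63 / sqrt(1 - r²).

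| r | Change score: d | Power, 40 per arm | Power, 50 per arm | T3 adjusted for T1: d | Power, 40 per arm |
|---|---|---|---|---|---|
| 0.2 | 0.498 | 59.5% | 69.4% | 0.643 | 81.1% |
| 0.3 | 0.532 | 65.2% | 75.1% | 0.660 | 83.1% |
| 0.4 | 0.575 | 71.9% | 81.3% | 0.687 | 85.9% |
| 0.5 | 0.630 | 79.5% | 87.7% | 0.727 | 89.5% |

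The variance ratio, change score to adjusted, is 2(1 - r)/(1 - r²) = 2/(1 + r). This exceeds 1 for any r below 1, so under these assumptions the adjusted comparison is always the more precise of the two.

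**The case against.** The strongest reply is that the plan contains no arithmetic error. The trial is sized on 0.63, which rests partly on external EGWG effects, and 40 per arm is right for that value. This stands. A reader might infer from the follow-up d of 0.55 that 0.69 was miscalculated. The documents do not support that: the plan calls the effect only roughly equivalent to 0.69, never defines it as a follow-up difference over its SD, and recognised difference-in-change definitions give values around it. A reader might also infer that the trial has 67% power instead of 80%. That does not follow either. The 67% needs a true effect of exactly 0.546, the full 20% attrition and no use of baseline data, and the pilot interval contains both 0.63 and 0.69. Nor does a self-reported pilot measure fix the power of a Fitbit outcome.

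It can also be said that section III already discloses the self-report and the missing EGWG data, and that the aims are feasibility and estimation. Both are true and limit the weight of the point. Section III also describes the pilot comparator in two ways, as an educational control group and as standard of care, so no weight is put on the comparator here.

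Finally, a growth model already uses T1. That is so, but its precision depends on how arm enters the intercept, and IV.F leaves this open.

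**Conclusion.** The sample size is correct as calculated. Two points remain.

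1. The pilot does not clearly show that 0.63 is conservative for the Fitbit outcome. The derivation of 0.69 is missing, the data shown give 0.55 to 0.71 depending on definition, and the measure and time point differ from those of the trial.
2. The Fitbit analysis can be made more precise at no cost. At d = 0.63 and 40 per arm, adjusting for T1 gives about 81% to 90% power for r from 0.2 to 0.5, against about 60% to 80% for a change-score model: a gain of roughly 22 points at r = 0.2 and 10 at r = 0.5.

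The second point rests on equal SDs, an assumed r, and the growth model being fitted with arm free on the intercept. If the arms are already meant to share a common T1 mean, the plan only needs to say so.

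**What to change.** In IV.F, state that the Fitbit comparison at T3 adjusts for the T1 Fitbit value, or that the growth model constrains the arms to a common T1 mean. Randomisation follows the T1 Fitbit week, so either is legitimate.

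In IV.B, keep 0.63 and present it as the effect detectable with 80% power at 40 analysed per arm. State how 0.69 was derived, and that the pilot activity data are self-reported total activity up to 3 months postpartum. Optionally add, labelled as a sensitivity figure, that at the pilot's follow-up d of 0.55 unadjusted power is about 67% with 40 analysed per arm and 77% with 50.

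The cost is one line in IV.F and two or three sentences in IV.B. The T1 data are already collected, and enrolment and procedures are unchanged.

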COMIRB Protocol

COLORADO MULTIPLE INSTITUTIONAL REVIEW BOARD
[name] [contact] [contact]

Protocol #: 19-1366

Project Title: My Baby My Move+

Principal Investigator: [name]

Version Date: 5.6.21

I. Hypotheses and Specific Aims:

Statement of Purpose: The proposed study will implement and test the feasibility of a theoretically-based (e.g., social cognitive theory), peer-led wellness intervention, “My Baby My Move+” (MBMM+) to reduce excessive gestational weight gain (EGWG) by targeting physical activity, mood, and sleep.

The aims of the proposed research are to:

- Aim 1. Determine feasibility (i.e., acceptability and demand) of the MBMM+ program.
- Aim 2. Examine the impact of the MBMM+ program on EGWG at 12 weeks post-baseline to determine estimates of effect size for a future, larger randomized trial.

II. Background and Significance:

Up to 50% of pregnant women in the U.S. gain weight in excess of the Institute of Medicine (IOM) guidelines (i.e., excessive gestational weight gain (EGWG)). EGWG leads to poor maternal (e.g., pre-eclampsia, gestational diabetes, postpartum weight retention) and child (e.g., preterm birth, large for gestational age weight at birth) outcomes. It also sets the stage for long-term overweight/obesity for both mother and child. There are few efficacious intervention strategies for reducing EGWG and among those, physical activity is one promising strategy. Prenatal physical activity is associated with a variety of health benefits (e.g., reducing risks for gestational diabetes, pre-eclampsia, depression, and body image dysphoria). There is also a need to increase prenatal physical activity as approximately 80% of pregnant women are not meeting recommended levels. One reason for low prenatal activity is that pregnant women are concerned with and lack knowledge/skills about how to safely and effectively participate in physical activity. Increasing knowledge and skills about physical activity may improve prenatal physical activity participation, lower safety concerns, and in turn, reduce EGWG.

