- The Study Coordinator will keep hand sanitizer in their car and use before and after delivery of assessment and programmatic materials.
- The research team will follow all safety protocols instituted by the University of Colorado regarding COVID-19 and human subjects research.

Weight Gain. Weight will be collected at T1 and T3 for all intervention and control participants. Participants will be asked to record their weight three times on one day and send a picture (via text or email) to a member of the research team during the 7-day assessment week. Individuals will be asked to remove their clothes and shoes and keep on their undergarments and weigh themselves first thing in the morning before they eat anything. Total GWG will be captured three times consecutively and then averaged across these three weight recordings. Total GWG will be compared to the IOM guidelines at T1

and T3 and calculated as: +, -, or 0 with respect to the guidelines (based on each woman's pre-pregnancy BMI-determined GWG category) such as GWG above the guidelines (+), below guidelines (-), or within the guidelines (0) [39]. Participants randomized to the intervention group will also be given a TANITA scale to measure weight at home daily (the research team will send weekly reminders via email or text). Women will step on the scale and note their weight on a tracking log at the same time each day. Participants will email copies of tracking logs weekly to the study coordinator. Please see appendix for tracking log.

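### The 80% power claimed for EGWG is a continuous-outcome figure; if EGWG is analysed as the category the plan defines, 40 per arm does not deliver it

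*Combined protocol and SAP*

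**What the plan says.** Section IV.B, Sample Size, sets the effect size: "we estimated effect size to detect effects of $d > .63$, a medium effect, for the proposed MBMM+ intervention". One of its two sources is a physical-activity result: "our preliminary work with the original MBMM showed an effect roughly equivalent to Cohen's $d = 0.69". The other is a cited range of effects on EGWG, whose scale is not given. From this effect size, with alpha 0.05 and power 0.80, the paragraph concludes that "a sample size of 40 per arm (80 total) would be adequate to detect medium effects in EGWG, exercise, and other outcomes". On enrolment it says: "We propose enrolling 50 per arm to account for up to 20% attrition", and adds that the larger number also leaves room for smaller EGWG effects.

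Section II introduces EGWG as weight gain beyond the guidelines: "Up to 50% of pregnant women in the U.S. gain weight in excess of the Institute of Medicine (IOM) guidelines". Section IV.A, Weight Gain, collects weight in triplicate at T1 and T3, averages it, and compares gain with the guidelines in three levels, "such as GWG above the guidelines (+), below guidelines (-), or within the guidelines (0".

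Section III says of the earlier MBMM pilot: "A major limitation to these data is that we did not collect data on EGWG".

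Section IV.F plans latent growth curve models for Fitbit exercise and for EGWG. It states neither a link function nor whether the EGWG outcome is weight or category. No section gives a control-arm EGWG rate, a target difference in proportions, or a power figure for a categorical outcome.

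**The concern.** Cohen's d is a difference in means divided by a standard deviation, and a sample size derived from it applies to an outcome measured on that scale. Cutting the same outcome into above, within or below a threshold discards information, so the same underlying effect is harder to detect with the same number of women. The plan states its power on the continuous scale and defines its outcome on the categorical one.

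EGWG is the only effectiveness outcome named in Aim 2, and a larger trial is to be planned from its estimates. Anyone who takes the definitions in sections II and IV.A at face value will attach 80% to a comparison that has less, and may carry that optimism into the next trial's sample size.

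**Working it through.** **Inputs from the protocol.** d = 0.63, alpha = 0.05, power = 0.80, 40 evaluable per arm, and 50 enrolled per arm with up to 20% attrition (IV.B). EGWG in up to 50% of US pregnant women (II). Sidedness is not stated; two-sided reproduces the plan's figure, and one-sided would give 32 per arm.

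**Assumptions, not in the protocol.** A control-arm EGWG rate: 50% as the base case, range 30% to 70%. The section II figure is a national upper figure, not a trial rate at 12 weeks. A conversion of d to proportions is also needed; two standard ones are shown.

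**Step 1. Reproduce the plan.** n per arm = 2(1.960 + 0.842)² / 0.63² = 39.6, rounded up to 40. Power at 40 per arm is 80.4% by the normal formula and 79.5% by the noncentral t. Allowing for attrition, 40 / 0.80 = 50. The stated numbers are correct for a continuous outcome.

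**Step 2. Convert d = 0.63 to an above-guideline rate, control 50%.**
- Normal shift: Φ(Φ⁻¹(0.50) − 0.63) = Φ(−0.63) = 26.4%.
- Logistic: odds ratio = exp(0.63 × π/√3) = exp(1.143) = 3.14. Treated odds = 1/3.14, so the rate is 1/(1 + 3.14) = 24.2%.

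**Step 3. Power of the yes/no comparison.** Uncorrected chi-square test, two-sided 0.05, by full enumeration of the two binomials, 40 per arm:

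| Assumed control rate | Treated rate, normal | Power | Treated rate, logistic | Power |
|---|---|---|---|---|
| 30% | 12.4% | 49.7% | 12.0% | 51.9% |
| 40% | 18.9% | 54.9% | 17.5% | 61.0% |
| 50% | 26.4% | 59.3% | 24.2% | 67.7% |
| 60% | 35.3% | 62.7% | 32.4% | 72.7% |
| 70% | 45.8% | 61.2% | 42.7% | 71.8% |

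Fisher's exact test is lower still: 50.2% and 59.1% at the 50% control rate.

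**Step 4. All 50 per arm retained, control 50%.** Power is 69.1% (normal) and 77.4% (logistic).

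**Step 5. What 40 per arm can detect as yes/no.** From a 50% control rate, a fall to 20.5% has 80.2% power and a fall to 20.6% has 79.9%. A fall to 40% has 15.7%.

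**Step 6. The three-level score kept as ordered.** Simulated Wilcoxon test, 40 per arm, with 40% to 50% of controls above and 10% to 30% below the guidelines (assumed): about 67% to 71% under the normal conversion and 76% to 78% under the logistic. Treating the levels as unordered (2-df chi-square) gives about 57% to 69%.

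**The case against.** The strongest reply is that the category may not be the analysed outcome. Averaged weights are collected at T1 and T3, and section IV.F puts EGWG in the same growth-curve sentence as a continuous Fitbit measure. If continuous weight gain is modelled, the 80% holds. This stands, and it makes the point conditional.

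Second, any single percentage for the category depends on a control rate, a conversion and a choice of levels that the plan does not give. Section IV.B's recruitment text also says that providers will help find women in need of EGWG intervention, so a control rate above 50% cannot be excluded. This stands too, which is why ranges are shown. At 40 per arm every categorical version tried still falls below 80%. With all 50 per arm retained, the logistic conversion at 60% to 70% does reach 81% to 82%.

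Third, an effect size of 0.63 read as Cohen's h, the arcsine difference between two proportions, would give 40 per arm directly: 2·arcsin√0.50 − 2·arcsin√0.205 = 0.63. But section IV.B states d, and draws it in part from a physical-activity effect, so the plan does not support that reading.

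Lastly, a reader might infer that a null result would be taken as ruling out a medium effect on EGWG. The documents do not say so. Aim 2 belongs to a feasibility study and seeks effect-size estimates for a later trial, which lowers the stakes without making the adequacy statement correct.

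**Conclusion.** The point holds in conditional form. The 80% is sound arithmetic for a continuous outcome, but it is claimed for an outcome that the protocol defines and scores only as a category, and the analysis section does not settle which is used.

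If the category is analysed, the shortfall at 40 evaluable per arm is about 12 to 21 percentage points for yes/no EGWG at an assumed 50% control rate (80 − 68 and 80 − 59). It is about 10 points for an ordered three-level analysis under the normal conversion, and smaller under the logistic. These sizes rest on the assumed control rate, the conversion of d and unadjusted tests; the covariate-adjusted growth model was not evaluated.

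It would be going too far to say that the EGWG power is wrong under any reading, or that one particular percentage is the trial's true power. The silence of section IV.F and the absence of a trial control rate rule out both statements.

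**What to change.** In section IV.B, limit the 80% power at d = 0.63 to continuous outcomes, including continuous weight change from T1 to T3, and name that change as the EGWG measure the figure refers to. State the same scale in section IV.F so that the two sections agree.

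If the category is to be analysed, replace the adequacy claim with power on that scale and label the assumptions. For example: at an assumed 50% control rate, 40 per arm has 80% power for a fall to about 20% to 21%, and about 59% to 68% for the effect equivalent to d = 0.63, depending on the conversion. If the three ordered levels are kept, give the ordinal figure instead.

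In either case, remove the claim that the size is adequate for medium effects on categorical EGWG. The change is wording only and needs no extra women or procedures; the downside is a less favourable stated power.
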